4.2 Subject Recruitment and Screening

Subjects will be voluntarily recruited from the Principal Investigator or Sub-Investigator population and/or referring physicians.

Subjects will be screened to determine if they meet all inclusion and no exclusion criteria. If all entry criteria are accomplished, the subject will be eligible to participate in the study.

Eligible subjects will be provided an IRB approved Informed Consent Form for review and signature. Each subject will have a physical assessment by the surgeon and will complete all patient reported outcomes (KOOS, VAS, IKDC subjective, Marx). X-rays and MRI will be attained if previous imaging is greater than 3 months old.

All potential subjects screened for eligibility will be listed on the electronic Screening and Enrollment Log. The electronic Screening and Enrollment Log will document the date of screening, the results of screening, and the primary reason for excluding the subject. The electronic Screening and Enrollment Log will be kept on the research shared drive (encrypted and located behind the OSUMC firewall). The log will be password protected.

4.3 Study Duration and Follow-Up

Study duration will be until the last subject enrolled reaches 52 weeks post-operative.

Subjects will be assessed pre-operatively and return post-operatively at Day 10, Weeks 6, 24, and 52. At follow-up visit Week 24, the subject questionnaires will be administered online through RedCap. At follow-up visits Week 6 and 52, the subject questionnaires will be administered in the office. At each follow up visit, AEs and concomitant medication will be reviewed, as applicable. At week 52 post-operatively, the subjects will complete a MRI of the treated knee.

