4. PROCEDURES

4.1 Research Design

This is a non-inferiority, prospective, single blinded, randomized, single-center study design with enrollment of 82 randomized subjects (to assure 70 subjects complete the study). The sample size of 82 participants was calculated from a power analysis. The study was powered to detect at least a seven point change in KOOS pain score based on achieving 80% statistical power to detect a non-inferiority margin. Study duration will be until the last subject enrolled reaches 52 weeks post-operative.

The 82 randomized subjects will be randomized at a 1:1 ratio into the Werewolf Coblation wand treatment group or mechanical debridement treatment group. Subjects will be blinded to their treatment assignment until they complete all study visits. Upon withdraw from the study, termination from the study, or new or recurrent symptoms requiring a subsequent arthroscopy, the blinded assignment will be revealed to the subject.

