4.5 Detailed Study Visits

Screening

- Confirm written informed consent prior to screening procedures
- Inclusion/exclusion criteria
- Physical assessment by surgeon – IKDC objective
- Demographics
- Medical and surgical history

- X-rays unless provided (must be less than 3 months old)
- MRI unless provided (must be less than 3 months old)
- Patient reported outcomes
 - KOOS, VAS, IKDC subjective, Marx

Date of surgery

- Arthroscopic inclusion/exclusion criteria
 - No articular cartilage lesion present that requires treatment
 - Evidence of previous chondral treatment not noted at screening
 - Chondrocalcinosi
- Randomization
- Surgery performed

10 days (7 days-14 days post op)

- Explanation of the weekly online data to be collected on RedCap
 - KOOS activity, VAS, return to work/activity (WPAI V2.0). [To be completed weekly from 1 week post op to 6 post op]
- Physical assessment by surgeon – IKDC objective
- Patient reported outcomes
 - KOOS, VAS, IKDC subjective, Marx

6 weeks (\pm 5 days)

- Physical assessment by surgeon – IKDC objective
- Patient reported outcomes
 - KOOS, VAS, IKDC subjective, Marx

6 months (\pm 14 days)- To be completed in RedCap

- Patient reported outcomes
 - KOOS, VAS, IKDC subjective, Marx

12 months (\pm 28 days)

- Physical assessment by surgeon – IKDC objective
- Patient reported outcomes
 - KOOS, VAS, IKDC subjective, Marx
- X-rays (merchant view, AP and PA Rosenberg)
- MRI

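### The protocol gives no remote route for the Week 52 KOOS when a subject does not attend, although the same forms already run in RedCap

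*Protocol*

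**What the plan says.** Protocol 2.1 makes the change in the KOOS activity subscale from baseline to Week 52 the primary endpoint, and 4.4 repeats the subscale.

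Protocol 4.3 assigns a mode of completion to the later visits. For the middle one: "At follow-up visit Week 24, the subject questionnaires will be administered online through RedCap". For the other two: "At follow-up visits Week 6 and 52, the subject questionnaires will be administered in the office".

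Protocol 4.5 agrees. Its 6-month entry lists KOOS, VAS, IKDC subjective and Marx and is marked "To be completed in RedCap". Its 12-month entry lists the same four questionnaires with the surgeon's examination, X-rays and MRI. It carries a window of ±28 days and no RedCap mark. The 10-day entry introduces early online collection ("Explanation of the weekly online data to be collected on RedCap"), whose content is "KOOS activity, VAS, return to work/activity (WPAI V2.0). [To be completed weekly from 1 week post op to 6 post op".

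On expected loss, 4.1 plans "enrollment of 82 randomized subjects (to assure 70 subjects complete the study".

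No section names an online, postal or telephone route for a subject who does not attend at Week 52.

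**The concern.** The KOOS is completed by the subject, and this trial already has it running online for everyone enrolled. At the one time point that carries the primary endpoint, the only stated mode is the clinic visit. That visit is also the follow-up visit with the most procedures. A subject who has moved away or does not wish to travel could still answer a questionnaire, but the plan as written does not ask for one.

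Two things are at stake. The first is precision, because fewer subjects have a Week 52 KOOS. The second is bias. Enrolling 82 to end with 70 protects the number of completers, but not against those 70 being a selected group. In a non-inferiority comparison, if subjects with poor results were lost more often from the radiofrequency arm, a comparison of completers would flatter that arm and favour a false conclusion of non-inferiority.

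An analysis plan can say how missing values are handled, but it cannot supply a questionnaire that was never sent. The mode of collection is a protocol matter, and this protocol fixes it.

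**Working it through.** **Modes side by side (Protocol 4.3 and 4.5)**

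- Weekly to Week 6: KOOS activity, VAS and WPAI, online in RedCap.
- Week 6: full set, in the office.
- Week 24 (6 months): full set, online in RedCap.
- Week 52 (12 months): full set, in the office, with no alternative stated.

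The forms, the platform and the subjects' use of it are therefore in place before Week 52. The ±28-day window helps a subject who attends late, but not one who stops attending.

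**The planned loss**

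Inputs from 4.1: 82 randomized, 70 completers.

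- Implied loss = (82 − 70)/82 = 12/82 = 14.6%.
- Check: 70/(1 − 0.146) = 82.0. The two figures agree with each other, but the check is circular because the rate comes from those same figures. The 70 itself cannot be reproduced, because 4.1 gives no standard deviation and no alpha.

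**Precision gained by recovery**

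With 1:1 allocation and a fixed standard deviation, the standard error of the arm difference is proportional to 1/√N. If r of the 12 are recovered, the ratio to the planned standard error is √(70/(70 + r)). The share recovered is an assumption, so the range is shown:

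- None: N = 70, ratio 1.
- A quarter (r = 3): √(70/73) = 0.979, a fall of 2.1%.
- Half (r = 6): √(70/76) = 0.960, a fall of 4.0%.
- All (r = 12): √(70/82) = 0.924, a fall of 7.6%. This is an upper bound that will not be reached, since some of the 12 will have withdrawn.

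**The same in power (illustration only)**

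Assumptions: margin 7 points, true difference 0, and the standard deviation solved so that 35 per arm gives 80% power, SD = 7/((z₁₋α + z₀.₈₀)·√(2/35)).

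- One-sided alpha 0.025: SD = 7/((1.960 + 0.842) × 0.239) = 10.45.
- One-sided alpha 0.05: SD = 7/((1.645 + 0.842) × 0.239) = 11.78.

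Power by number with a Week 52 KOOS, at alpha 0.025 and 0.05 respectively:

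- 60: 73.7% and 74.4%
- 66: 77.6% and 77.9%
- 70: 80.0% and 80.0%
- 74: 82.1% and 81.9%
- 78: 84.1% and 83.6%
- 82: 85.8% and 85.2%

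Each four subjects recovered above 70 add about 2 percentage points. A fall to 60 costs about 6.

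**Bias**

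If a share p of an arm is missing and those subjects average d points below the completers, the completers' mean is too high by p × d. The error in the arm difference is the difference between the two arms' products.

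- Equal loss and equal deficit in both arms: error 0.
- Assumed 20% against 10% missing, deficit 10 points in both: 0.20 × 10 − 0.10 × 10 = 1.0 point.
- The same with half of the missing recovered at random. In the 20% arm the error becomes 2 − (0.10/0.90) × 10 = 0.889. In the 10% arm it becomes 1 − (0.05/0.95) × 10 = 0.474. The remaining error is 0.415 point. Simply halving both missing shares gives 0.5. Either way, roughly half of the error goes.

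The protocol supplies neither p by arm nor d, so these lines show the mechanism and are not an estimate.

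**The case against.** The strongest reply is that this is a coherent choice. Sections 4.3 and 4.5 agree. Baseline questionnaires are completed at screening alongside the surgeon's assessment, so they were probably done in person, although their mode is not stated. Office completion at Week 52 would then match the mode at both ends of the change score. The online collections are interim ones and do not show that mixed mode is harmless at the primary time point. This part stands: it is a reason to keep the office as the default, and it makes mixed mode a real, if small, cost. It is not a reason to prefer no value to one obtained online.

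It can also be said that the protocol does not prohibit another route, and that the site may have procedures for contacting non-attenders that are not shown. That is fair. That the office is the only route is an inference from its being the sole mode stated, in contrast to Week 24.

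A reader might infer that declining the MRI or X-rays forfeits the primary outcome. The protocol does not support that. Section 4.5 lists the questionnaires and imaging as separate items, and nothing makes one conditional on the other. A subject who attends and refuses the MRI can still complete the KOOS. The loss arises only from not attending.

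A reader might also set the 1-point error against the seven points in 4.1 and report a bias of 1/7, about 14%. That does not hold up. The twofold imbalance in loss is assumed, subjects are blinded to allocation, and equal loss with equal deficits gives no bias. Even on those assumptions, recovering half of the missing removes only about half of the error. The seven points are also stated for KOOS pain, not the activity subscale, and are not clearly identified as the non-inferiority margin.

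**Conclusion.** The point holds as an avoidable weakness in how the primary endpoint is collected. It is not a contradiction or a calculation error. As written, a subject who does not return at Week 52 has no stated way to give the primary outcome, although the trial already collects the same questionnaire online.

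The size is modest and partly unknown. Planned non-completion is 14.6%. The protocol does not break it down by cause, so the recoverable share cannot be derived. Recovery of half, an assumption, would lower the standard error by about 4%. The power figures rest further on a 7-point margin, a true difference of 0 and a back-solved standard deviation. Selective loss could bias the comparison, but the document supports no figure for that bias. Nor does it show that subjects are likely to refuse the Week 52 visit; it shows only that this visit has the most procedures.

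**What to change.** Amend Protocol 4.3 and the 12-month entry in 4.5:

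- Keep office completion as the default at Week 52.
- Send any subject who does not attend and has not withdrawn consent the same KOOS, VAS, IKDC subjective and Marx forms through RedCap, within the existing ±28-day window.
- Record the mode of completion for each Week 52 questionnaire, so that its influence can be examined.

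The cost is a short amendment and reuse of forms already built, with no new procedure. The downside is mixed completion mode for a few subjects at the primary time point. The IKDC objective examination, X-rays and MRI still need attendance and stay missing for these subjects.

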4.4 Measurement/Instrumentation

The change in the KOOS activity subscale will be the primary study endpoint. Secondary outcomes include time to return to work/activity and time to return to no pain. Baseline MRI will be compared to MRI at 52 weeks to evaluate knee morphology, cartilage signal, osteophytes, bone marrow edema, subarticular cysts, effusions and loose bodies. The international cartilage repair score will be used.

4.5 Detailed Study Visits

Screening

- Confirm written informed consent prior to screening procedures
- Inclusion/exclusion criteria
- Physical assessment by surgeon – IKDC objective
- Demographics
- Medical and surgical history

- X-rays unless provided (must be less than 3 months old)
- MRI unless provided (must be less than 3 months old)
- Patient reported outcomes
 - KOOS, VAS, IKDC subjective, Marx

Date of surgery

- Arthroscopic inclusion/exclusion criteria
 - No articular cartilage lesion present that requires treatment
 - Evidence of previous chondral treatment not noted at screening
 - Chondrocalcinosi
- Randomization
- Surgery performed

10 days (7 days-14 days post op)

- Explanation of the weekly online data to be collected on RedCap
 - KOOS activity, VAS, return to work/activity (WPAI V2.0). [To be completed weekly from 1 week post op to 6 post op]
- Physical assessment by surgeon – IKDC objective
- Patient reported outcomes
 - KOOS, VAS, IKDC subjective, Marx

6 weeks (\pm 5 days)

- Physical assessment by surgeon – IKDC objective
- Patient reported outcomes
 - KOOS, VAS, IKDC subjective, Marx

6 months (\pm 14 days)- To be completed in RedCap

- Patient reported outcomes
 - KOOS, VAS, IKDC subjective, Marx

12 months (\pm 28 days)

- Physical assessment by surgeon – IKDC objective
- Patient reported outcomes
 - KOOS, VAS, IKDC subjective, Marx
- X-rays (merchant view, AP and PA Rosenberg)
- MRI

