2.2 Secondary Endpoints

- Change in Visual Analogue Scale (VAS) scores from baseline
- Change in International Knee Documentation Committee (IKDC) Subjective Knee Evaluation Form scores from baseline
- Change in International Knee Documentation Committee (IKDC) Objective Knee Examination Form scores from baseline
- Change in Marx Activity Rating Scale from baseline
- Change in Work Productivity and Activity Impairment Questionnaire for Articular Cartilage Knee Injuries V2.0 (WPAI V2.0) from 1 week post-op to 6 weeks post-op
- Subject Satisfaction at Week 52 post-op

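### The weekly RedCap entries are explained only at the 10-day visit, after the 1-week entry that starts the WPAI endpoint falls due for anyone seen later than day 7

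*Protocol*

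**What the plan says.** Protocol section 4.5 lists the content of each visit. Under the visit headed "10 days (7 days-14 days post op" it has the item "Explanation of the weekly online data to be collected on RedCap". The content of those entries is given as "KOOS activity, VAS, return to work/activity (WPAI V2.0", and their timing as "To be completed weekly from 1 week post op to 6 post op". The screening and date-of-surgery lists in the same section mention neither RedCap nor the weekly entries.

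Section 2.2 defines one secondary endpoint as the change in "WPAI V2.0) from 1 week post-op to 6 weeks post-op". Section 4.3 says that subjects "return post-operatively at Day 10, Weeks 6, 24, and 52", so no post-operative contact is scheduled before the 10-day visit.

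At screening, section 4.2 has subjects "complete all patient reported outcomes (KOOS, VAS, IKDC subjective, Marx", and section 4.5 repeats those four instruments for the office part of the 10-day visit. WPAI is in neither list. The protocol gives no due day and no completion window for the weekly entries.

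**The concern.** The first weekly entry is the starting value of the WPAI endpoint. The protocol has subjects told about the weekly entries at a visit that can fall no earlier than the day the first one becomes due, and nominally falls after it. A subject who follows the schedule as written and is seen after day 7 has not yet been told to make an entry when the first week ends.

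That leaves two outcomes. Either the Week 1 WPAI value is absent, or it is entered at or after the visit and labelled Week 1 although it was given at some point up to day 14 or later. In the first case the subject has no change score as defined. In the second the change covers a shorter stretch of recovery, and how much shorter depends on the visit date. A Week 1 value that was not collected on time cannot be collected later. Visit content belongs in the protocol, so this does not depend on what a statistical analysis plan might add.

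**Working it through.** There is no stated figure to reproduce; the check is a day count on the protocol's own schedule.

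**Inputs**
- Start of weekly entries: 1 week post-op (section 4.5), read as day 1 × 7 = 7.
- End of weekly entries and of the WPAI endpoint: 6 weeks (sections 2.2 and 4.5), read as day 6 × 7 = 42.
- Visit at which the entries are explained: nominal day 10, window days 7 to 14 (section 4.5).

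Reading the week labels as exact days is an assumption, because the protocol does not state a due day.

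**Lag between due day and explanation**
- Permitted visit days: 14 − 7 + 1 = 8.
- Visit days later than day 7: days 8 to 14, which is 7 of the 8.
- Nominal visit: 10 − 7 = 3 days, or 3/7 = 43% of the weekly interval.
- Last permitted day: 14 − 7 = 7 days, when the Week 2 entry is itself due.

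**Span of the WPAI change if the first entry is made at the visit and the last on day 42**
- Visit on day 7: (42 − 7)/7 = 5.0 weeks.
- Visit on day 10: (42 − 10)/7 = 4.6 weeks.
- Visit on day 14: (42 − 14)/7 = 4.0 weeks.

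**The same count under a looser reading.** If a Week 1 entry may be made on any of days 7 to 13, a visit on 7 of the 8 permitted days (7 to 13) still allows one, and only a day-14 visit does not. The entry is then not missing, but its timing moves with the visit date.

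**Is there a substitute value?** Comparing the visit lists in section 4.5:
- WPAI: not at screening and not among the office questionnaires at 10 days. The first weekly entry is the only scheduled source of the Week 1 value.
- KOOS and VAS: collected at screening and again at the 10-day visit, so an early post-operative value exists even if the first weekly entry is lost.
- Primary endpoint (section 2.1): KOOS activity subscale at Week 52 against baseline. It uses no weekly entry.

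These are counts of permitted days, not of subjects. The protocol does not say how visits will be spread over the window, so the share of the 82 subjects affected cannot be calculated.

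**The case against.** The strongest reply is that the day-7 deadline is the reader's and not the protocol's. The text says weekly from 1 week and gives no entry window. The visit window opens exactly at 1 week, which fits an intention to make the first entry at or around that visit. This stands in part: a subject seen on day 7 can enter on time, and a later entry could be accepted as Week 1. So a reader might infer that the Week 1 value will be missing or late throughout, but the document supports only that it may be, for subjects seen after day 7. Accepting late entries does not remove the problem, because the starting point then differs between subjects.

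It can also be said that section 4.5 is a terse checklist that does not forbid earlier set-up or prompts, and that the consent form, which is not shown, may describe the weekly entries. That is possible. But the protocol schedules the explanation at one visit only, and that visit is too late for most of its window.

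Three wider inferences are tempting and are not supported:
- **Loss across all weekly instruments.** KOOS and VAS are collected at the 10-day visit in any case.
- **Harm to time to return to work/activity and time to no pain.** Section 4.4 names both but does not say how either is derived. The label on the WPAI item makes the link to work plausible; the link to pain is an assumption.
- **Bias between the arms.** The schedule is the same in both arms and subjects are blinded (section 4.1). Nothing in the document suggests that late first entries would differ by treatment.

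**Conclusion.** The point holds in a limited form. Followed as written, section 4.5 tells subjects about the weekly entries after day 7 on 7 of the 8 permitted visit days, by 3 days at the nominal visit and by up to 7 days. The consequence is a Week 1 WPAI value that may be missing, or recorded at a time varying up to day 14, so that a nominal 5-week change can shrink to 4.6 or 4.0 weeks. No other scheduled WPAI value can stand in for it.

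The exposure is essentially one of the six listed secondary endpoints. The primary endpoint is unaffected, and no effect on the treatment comparison has been shown. The day counts rest on reading 1 week as day 7 and 6 weeks as day 42. Under a looser entry window the main effect is variable timing, with fewer missing values. The change is worth making because it is nearly free and the value cannot be recovered afterwards.

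**What to change.** In section 4.5, move the RedCap explanation and set-up from the 10-day visit to screening or the date of surgery. Send the first prompt on day 7. Keep an item at the 10-day visit to check that the first entry was made. Record the actual date of every weekly entry, so that the true interval of each WPAI change is known.

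A rule that sets late first entries to missing, for example any made after day 9, should not be added. The cut-off would be arbitrary, and if the explanation still slipped to the visit it would discard entries made on the nominal day 10, creating the gap the change is meant to prevent.

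The cost is one item moved in the visit list, a prompt date in RedCap and a few minutes per subject before or on the day of surgery. No visit is added and no treatment rule changes.

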4.6 Data Analysis and Study Validity

We will minimize selection bias by including a consecutive series of eligible cases until the sample size is achieved. Data will be analyzed using standard statistical software, STATA 13 (College Station, Tx). Descriptive statistics will be generated for the total sample. We will assess the difference in our primary and secondary outcomes.

5 SELECTION OF SUBJECTS

Subjects who meet all of the following criteria will be voluntarily recruited by participating Investigators:

5.3 Inclusion Criteria

Subjects MUST meet ALL of the following criteria to be included in the study:

- Given written informed consent on the IRB approved consent form specific to the study, prior to study participation
- 18-50 years old
- Male or Female
- Suspected chondral damage in the following locations where debridement is indicated:
 - Medial femoral condyle
 - Lateral femoral condyle
 - Trochlea
 - Patella
- < 30% joint space narrowing as seen on x-ray (merchant view, AP and PA Rosenberg)
- 1 or more chondral lesion(s) as noted on MRI
- Concomitant procedures are allowed unless noted in the exclusion criteria

5.4 Exclusion Criteria:

- Previous chondral treatment in the same compartment (prior debridement and lavage performed more than *three* months prior to baseline are acceptable)
- Focal chondral defect indicated for concomitant procedures (i.e., microfracture, ACI, MACI, OATs)
- Concomitant procedures that are not allowed:
 - Lateral retinacular release
 - Excision of osteophytes
 - Subchondroplasty
 - Manipulation under anesthesia
 - ACL reconstruction
 - Quad tendon repair
 - Patellar tendon repair
 - Patellar tendon debridement
 - Multiligament reconstruction
- Pregnant and/or intending to become pregnant during this study period

